1.0 Introduction

1.1 Study Conduct

This study will be conducted in compliance with the protocol approved by the Institutional Review Board, and according to Good Clinical Practice standards. No deviation from the protocol will be implemented without the prior review and approval of the IRB except where it may be necessary to eliminate an immediate hazard to a research subject. In such case, the deviation will be reported to the IRB according to its policies and procedures.

1.2 Background

Osteoarthritis (OA) is a common and major cause of pain and disability. An estimated 26.9 million adults in the US suffer from OA (1) and nearly 50% of adults may develop symptomatic knee OA by age 85 (2). Knee OA affects obese individuals at a higher rate with $\frac{2}{3}$ of individuals developing symptomatic disease. The treatment for knee osteoarthritis is broad and includes: exercise and patient education; pharmacologic therapies, including oral, topical, and intra-articular medications; and surgical interventions, including total joint arthroplasty. Minor symptoms can be managed with non-opioid pain medications such as acetaminophen or nonsteroidal anti-inflammatory drugs (NSAIDs), which are the mainstay of pain management for OA. Severe and end-stage osteoarthritis can be treated with total joint arthroplasty. Unfortunately, NSAIDs can be a cause of renal failure, exacerbation of asthma and most notably, gastrointestinal hemorrhage. Estimated number of deaths from NSAID-related gastrointestinal bleeding has been estimated at 16500 (3). With the significant morbidity associated with treatment of OA, there is a need to develop a new, effective, minimally invasive and safe treatment for pain related to osteoarthritis of the knee.

The principal symptom of OA, pain, is mediated by a number of factors. However, angiogenesis resulting in neovascularity, neural sensitization and inflammation has been described as a potential pathophysiological pathway of the deep joint pain described by many OA patients (4, 5). This increased vascularity in the setting of pain and OA has been the focus of recent endovascular investigation, with the proposed mechanism of embolization as a novel treatment.

Particulate embolization of geniculate artery branches supplying hypervascular joint tissue, the same technique we are proposing to treat pain from OA, has been previously described as a safe treatment for hemorrhage after total knee arthroplasty in multiple reports (6-9). In 2008, three cases were reported using 150-355 micrometer particles without any complications (6). In 2013, a Japanese group reported the use of 1000-2000 micrometer particles in the treatment of five patients, again without complication (9). In 2015, an author group that includes one of the Co-PIs reported outcomes from 13 cases in which there were no major complications and two minor complications (transient cutaneous ischemia) (8). Finally, in 2016 a fourth report of 14 embolizations was published in which there were no major complications and, again, two minor complications (transient cutaneous ischemia) (7).

Embolization of hypervascular joint tissue for the treatment of pain has been pioneered by [name] and his colleagues in Japan. They initially reported a case series in which they were able to reduce pain related to refractory tendinopathy and enthesopathy in multiple joints in 7 patients using an antibiotic particulate for embolization without major complication (10). Subsequently, the same team published its experience with transcatheter embolization of hypervascular tissue within the shoulder joint in 7 patients diagnosed with adhesive capsulitis. The procedure successfully resulted in pain reduction with any complications (11). Finally, Okuno et al also published their results after synovial embolization in patients with painful OA. The procedure was performed on 14 patients and there were no major complications. There was significant pain reduction and decreased difficulty of movement at 4 months. Medication frequency also decreased after embolization (12).

The current investigation teams have led efforts pioneering embolization procedures in novel targets that have proved successful (13-18). We have also had experience in embolization of the knee, in particular with post-arthroplasty hemorrhage (8). With our proven experience in embolization, and in particular the local-regional anatomy, we have set forth to pursue a US study evaluating embolization as a treatment for OA related knee pain.

1.3 Medical Device

1.3.1 Name of Investigational Device

Embozene Microspheres

1.3.2 Intended Use of the Investigational Device

Embozene Microspheres will be used for geniculate artery embolization (GAE) in subjects with knee osteoarthritis.

1.3.3 Description of the Investigational Device

CeloNova BioSciences Inc. Embozene® Microspheres and Embozene® Color Advanced Microspheres were found to be substantially equivalent and cleared medical devices (Premarket Notification K073417) to prior technologies:

- Boston Scientific Contours SE™ Microspheres (K032707), and
- Biocompatible Bead Block™ Microspheres (K033761).

Identified in the Code of Federal Regulations 21 Part 870- Subpart D- Cardiovascular Prosthetic Devices.

Classification Name: Artificial Embolization Device. Class II Medical Device
Common Name: Vascular Embolization Device Subpart D-Prosthetic Devices;
Sec. 870.3300

Indication for Use: A vascular embolization device is an intravascular implant intended to control hemorrhaging due to aneurysms, certain types of tumors (e.g.,

nephroma, hepatoma, uterine fibroids), and arteriovenous malformations. This does not include cyanoacrylates and other embolic agents, which act by polymerization or precipitation. Embolization devices used in neurovascular applications are also not included in this classification.

Embozene Microspheres are tightly calibrated, sub-millimeter, hydrogel beads coated with inorganic perfluorinated polymer coating for biocompatibility. They are manufactured in multiple sub-millimeter sizes. They come in a liquid suspension that is mixed with iodinated contrast before use. Once a catheter has been fluoroscopically guided into the target vessel, the microspheres are then injected, causing obstruction at the arteriole level until the desired degree of embolization has occurred. The microspheres used during the study will be unchanged.

1.4 Preclinical Data

Embozene Microspheres have proven to be an effective embolization material with high biocompatibility in multiple non-human studies (19-23). In porcine model studies, Embozene Microspheres effectively embolized renal arteries without toxicity, with low immunoreactivity and associated inflammation of the surrounding tissue and with low rates of recanalization. Inflammation within porcine liver models was also seen to be low after Embozene embolization.

1.5 Clinical Data to Date

Embozene Microspheres have been safely used as an embolic agent to target hypervascular lesions throughout the body including hepatocellular carcinoma, meningioma, uterine fibroids and adenomyosis and benign prostatic hyperplasia (18, 24-26). The investigators have also performed GAE for knee hemarthrosis with technical and clinical success using Embozene Microspheres (8). Recently, Embozene has been used safely and effectively for GAE to treat medial knee pain in the setting of osteoarthritis (12). Embozene Microspheres are FDA approved for the treatment of arteriovenous malformations and hypervascular tumors.

2.0 Study Objectives

The primary aims of this study are to determine if GAE will reduce the severity of pain as well as global disability (resulting from the combination of pain, stiffness and difficulty performing daily activities) caused by knee OA and if it can be performed safely. The secondary aim is to determine if GAE can result in the decreased necessity for ongoing conservative OA therapies such as medication therapy and joint injections. Another secondary aim to provide 'sample size data' for planning a future study.

3.0 Study Design

3.1 General Design

This will be an open label pilot study with a small population undergoing GAE to determine safety and efficacy. After IRB approval of a written informed consent and over, approximately a 24 month duration, N=20 subjects will be recruited within 2 hospital clinic based settings. Only subjects ≥ 40 years will be screened for study recruitment and will be un-blinded from study treatment. Clinical procedures and

evaluations will consist of a preoperative screening assessment to determine if the potential study subject meets the inclusion and exclusion criteria, enrollment, surgical procedure for geniculate artery embolization, and follow-up visits at 24 hours, 1, 3 & 6 months. An MRI will be performed at the 1-month visit to detect a change in synovial vascularity and to exclude complication.

3.2 Primary Study Endpoints

1. Overall efficacy of treatment as determined by a minimal clinically significant reduction in global Western Ontario and McMaster University Osteoarthritis Index (WOMAC) questionnaire scoring of 16% (27) at 6 months follow-up.
2. Minimal clinically important decrease of 15% on the pain VAS (28) at 6 month follow-up.

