3.3 Secondary Study Endpoints

1. Reduction of previously initiated OA medical therapy (e.g. NSAIDs) at 6 months follow-up.

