4.3 Inclusion Criteria

1. Moderate to severe knee pain (VAS > 50 mm), and
2. Pain refractory to at least 3 months* of conservative therapies (anti-inflammatory drugs, or physical therapy, or muscle strengthening, or intra-articular injections), and
3. Kellgren-Lawrence grade 1, 2 or 3 on radiograph of the knee.
4. Age > 40 years.

*3 months was chosen because this time interval is thought adequate for knee pain to be considered refractory to conservative care.

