7.2 Effectiveness Assessments

Technical success will be defined as devascularization of hypervascular synovium at the affected knee. This will be determined during the procedure. Clinical success will be defined as a 16% reduction of the baseline global WOMAC score at 6 month follow-up (primary outcome) and a 15% reduction of the baseline pain VAS score at 6 month follow-up (secondary outcome).

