8.0 Statistical Plan

8.1 Sample Size Determination

Only one small study has examined the use of transcatheter arterial embolization for the treatment of knee pain secondary to OA (12). In that study, the baseline WOMAC total score (mean±SD) was 48.5±9.4. The primary outcome of this study is a 16% reduction in the baseline WOMAC total score. Using the baseline total score from that study, a sample size of 15 will have 80% power to detect a 16% difference (7.8 points) in means, assuming a standard deviation of 10 points. Conservatively, to protect against a potential lost-to-follow-up of 30%, 20 total subjects will be enrolled. This sample size also will ensure adequate power for the secondary outcome, a reduction in the VAS by 15% at 6 months follow-up.

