8.2 Statistical Methods

This is a pre-post analytical design and the primary statistical method will be a paired t-test, examining changes from baseline to 6 months. We will use a paired t-test to statistically measure changes resulting from the GAE procedure. Frequencies, including pre-post change, will be reported as percents with 95% confidence intervals. Continuous data will be reported as means with 95% confidence intervals. $P \leq 0.05$ will be considered to indicate statistical significance. All analyses will be performed using SAS software and confidence intervals will be reported as appropriate, including estimates for the appropriate sample size for a larger future study (v9.2, SAS Institute Inc., Cary, NC).

Any deviations from the previously described statistical plan will be described and justified in a protocol amendment and/or in the final report submitted to the IDE application. The causes of all missing values will be documented with the study data.

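### The 6-month pain VAS is a primary endpoint in section 3.2 but the secondary outcome in sections 7.2 and 8.1, and section 8.2 does not settle which applies

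*Combined protocol and SAP*

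**What the plan says.** Two groups of sections give the VAS different standing.

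- **Section 3.2** numbers two primary endpoints: a 16% reduction in global WOMAC at 6 months and "Minimal clinically important decrease of 15% on the pain VAS (28) at 6 month follow-up".
- **Section 3.3** has a single secondary endpoint, "Reduction of previously initiated OA medical therapy (e.g. NSAIDs) at 6 months follow-up". The VAS is not there.
- **Section 2.0** leans the same way as 3.2: "The primary aims of this study are to determine if GAE will reduce the severity of pain as well as global disability". It names no instrument for pain.
- **Section 7.2** defines clinical success by a 16% WOMAC reduction and a 15% VAS reduction, and ranks them: "primary outcome) and a 15% reduction of the baseline pain VAS score at 6 month follow-up (secondary outcome".
- **Section 8.1** uses the singular: "The primary outcome of this study is a 16% reduction in the baseline WOMAC total score". It sizes the trial on WOMAC, then claims "adequate power for the secondary outcome, a reduction in the VAS by 15% at 6 months follow-up" without giving a VAS mean or SD.
- **Section 8.2** makes a paired t-test of the change from baseline to 6 months the primary method. A P value of 0.05 or less "will be considered to indicate statistical significance". It does not say which endpoint the primary test belongs to, in what order the scales are tested, or whether one or both must succeed.

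**The concern.** One measure at one visit has two ranks, and nothing in the plan says which section governs. This does no harm when both scales succeed or both fail. When they split, whoever writes the report can choose the section that suits the result. The study is single-arm and open-label (sections 3.1, 5.2 and 5.5), so nothing in the design prevents that choice from being made after the data are seen. The study is also meant to supply planning data for a later trial (section 2.0), and its planners need to know which endpoint this one was judged on.

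**Working it through.** **Step 1: the plan's own figure.** Inputs from 8.1: baseline WOMAC 48.5, reduction 16%, SD 10, n=15. Alpha is 0.05 from 8.2, taken as two-sided because no side is stated.

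- Difference: 0.16 × 48.5 = 7.76, which the plan rounds to 7.8.
- Standardised effect: 7.8 / 10 = 0.78.
- Noncentrality: 0.78 × √15 = 3.02; critical t on 14 df = 2.145.
- Exact power of the paired t-test (noncentral t): 80.2%, and 15 is the smallest n that reaches 80%.

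The WOMAC calculation in 8.1 reproduces. It stays correct whichever rank the VAS has.

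**Step 2: the verdict under each section.** Here a scale succeeds if it meets whatever criterion is applied to it.

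| Result | Under 8.1, and the item ranked primary in 7.2 | Under 3.2 |
|---|---|---|
| Both succeed | Met | Both primary endpoints met |
| WOMAC only | Met | One of two primary endpoints unmet |
| VAS only | Missed | Could be reported as a met primary endpoint |
| Neither | Missed | Neither met |

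The two middle rows are where the sections part. This needs no assumption about effect sizes.

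**Step 3: how often the scales might split (illustration).** The documents give no VAS mean, SD or correlation with WOMAC. Assume that the VAS has the same standardised effect, 0.78, and that changes are bivariate normal with correlation r. Take n=15 (the powered number in 8.1) and n=20 (all enrolled subjects complete, as 4.2 anticipates). Two paired t-tests, two-sided 0.05, 200,000 simulated trials per setting:

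| n | r | Both significant | Exactly one | Neither |
|---|---|---|---|---|
| 15 | 0 | 64.4% | 31.6% | 4.0% |
| 15 | 0.5 | 68.5% | 23.4% | 8.1% |
| 15 | 0.9 | 75.0% | 10.5% | 14.5% |
| 20 | 0 | 83.1% | 16.1% | 0.8% |
| 20 | 0.5 | 84.8% | 12.6% | 2.6% |
| 20 | 0.9 | 88.0% | 6.0% | 6.0% |

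Check at r=0, where exactly one is significant with probability 2p(1 − p): n=15 gives 2 × 0.802 × 0.198 = 0.318, and n=20 gives 2 × 0.911 × 0.089 = 0.162. Both agree with the simulation.

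These figures concern significance of the mean change, which is the test in 8.2. They do not measure how often the 16% and 15% thresholds would disagree.

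**The case against.** The best reply is that this is a 20-subject pilot, that 7.2 and 8.1 agree on WOMAC, and that the only power calculation is for WOMAC, so the intention is clear enough. Much of that stands. It is the reason to resolve the conflict towards WOMAC, and it makes a formal testing sequence optional. It does not remove the conflict. The section whose purpose is to list primary endpoints lists the VAS, and the plan sets a powered sample size and a significance level.

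A reader might also infer more than the documents support:

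- *That 2.0 makes the VAS primary.* It makes pain severity a primary aim but does not name the VAS, and by 6.1 WOMAC also reflects pain. Section 2.0 is consistent with 3.2 and goes no further.
- *That WOMAC alone is clinical success under 7.2.* Section 7.2 joins the two thresholds with a conjunction and can be read as requiring both. WOMAC alone meets the item ranked primary there; no more can be said.
- *That the error rate is inflated to 7% to 10%.* At independence, 1 − 0.95² = 9.75%. But this assumes that either scale suffices, which no section states, and it counts significant worsening. For false improvement alone, the same rule gives 1 − 0.975² = 4.9% at independence and 3.6% at r=0.9.
- *That power for success on both scales is very low.* Any such figure depends on the VAS mean and SD chosen, and the plan gives neither.

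**Conclusion.** The plan contradicts itself on the rank of the pain VAS: 3.2 and 3.3 on one side, 7.2 and 8.1 on the other, with 8.2 silent. The consequence is that a split result has no single primary verdict. That conclusion rests on the text alone.

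How often a split would occur cannot be known from the documents. With an assumed VAS effect of 0.78 and correlation 0 to 0.9, the t-tests disagree in about 11% to 32% of trials at n=15 and 6% to 16% at n=20. A different VAS effect would change these figures. The WOMAC sample size is not in question. Whether the primary outcome is judged by significance of the mean change or by the 16% threshold is a separate matter, which this point leaves open. The conflict should be corrected before analysis.

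**What to change.** - **3.2 and 3.3:** keep global WOMAC at 6 months as the sole primary efficacy endpoint and move the 15% VAS decrease to 3.3, which matches 7.2 and 8.1.
- **8.2:** name WOMAC as the endpoint of the primary paired t-test. State that the VAS result is secondary and cannot by itself establish that the primary endpoint was met. Testing the VAS only after a significant WOMAC result is an option.
- **7.2:** report the WOMAC and VAS responder definitions separately.

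Section 2.0 names no instrument and need not be rewritten. The change is to wording only: visits, data, sample size and WOMAC power stay as they are. The price is that the VAS can no longer be claimed as a stand-alone primary result.

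If the sponsor wants both scales as primary, 7.2 and 8.1 must be changed to say so, with a rule that both are required. Section 8.1 must then restate the joint power from a justified VAS mean and SD. Under the equal-effect assumption above, that power would be about 64% to 75% at n=15 rather than 80%.

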3.3 Secondary Study Endpoints

1. Reduction of previously initiated OA medical therapy (e.g. NSAIDs) at 6 months follow-up.

3.4 Primary Safety Endpoints

1. GAE without major complication.

4.0 Subject Selection and Withdrawal

4.1 General Characteristics of the Proposed Subject Population

Study subjects will be men and women with knee osteoarthritis resulting in knee pain that is refractory to conservative therapies, who are not planning to undergo surgery within 6 months.

4.2 Anticipated Number of Research Subjects

Enrollment into the investigation will be defined as providing informed consent for study participation per IRB policies.

Twenty (20) subjects will be enrolled between both sites and all are anticipated to complete the study.

4.3 Inclusion Criteria

1. Moderate to severe knee pain (VAS > 50 mm), and
2. Pain refractory to at least 3 months* of conservative therapies (anti-inflammatory drugs, or physical therapy, or muscle strengthening, or intra-articular injections), and
3. Kellgren-Lawrence grade 1, 2 or 3 on radiograph of the knee.
4. Age > 40 years.

*3 months was chosen because this time interval is thought adequate for knee pain to be considered refractory to conservative care.

4.4 Exclusion Criteria

1. Current local infection, or
2. Life expectancy less than 6 months, or

3. Known advanced atherosclerosis, which is known lower extremity vascular or lower extremity symptoms thought to be secondary to arterial vascular disease (eg claudication, ischemic rest pain), or
4. Rheumatoid or infectious arthritis, or
5. Prior knee surgery, or
6. Uncorrectable coagulopathy including INR > 2.5 or platelets < 30,000, or
7. Iodine allergy resulting in anaphylaxis, or
8. Renal dysfunction as defined by GFR (eGFR) of <45 obtained within the past 60 days, or
9. Contraindication for MR Imaging (such as claustrophobia, metallic fragment or foreign bones, implants or prosthesis), or
10. IV contrast allergy characterized by anaphylaxis or anaphylactoid reactions.

4.5 Subject Recruitment and Screening

Subjects will be recruited from orthopedic and interventional radiology clinics at University of North Carolina Healthcare System and the Vascular Institute of Virginia.

4.6 Early Withdrawal of Subjects

4.6.1 Criteria for Removal from Study

1. Subjects will be withdrawn from the study if
 - a. a major complication occurs that prevents completion of GAE or the ability to complete the follow up visits, or
 - b. at any point at their discretion.

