4.6.2 Follow-up for Withdrawn Subjects

If a subject withdraws from the study, any recorded data will still be included in the analysis. Subjects will only be replaced if they withdrew prior to undergoing GAE.

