6.5 Visit 5 - 3 Month Follow-Up

Subjects will be seen in clinic or contacted by phone or by teleconference per the subject's preference 90 +/- 10 days following GAE. The WOMAC questionnaire and VAS pain score will be completed and subjects will be evaluated for possible adverse events. Subjects will also provide an update about the necessity/frequency of pre-established conservative therapies. If AE is suspected based on change in pain scores or functionality, an MRI will be obtained for further evaluation.

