6.6 Visit 6 - 6 Month Follow-Up

Subjects will be seen in clinic or contacted by phone or by teleconference per the subject's preference 180 +/- 10 days following GAE. The WOMAC questionnaire and VAS pain score will be completed and subjects will be evaluated for possible adverse events. Subjects will also provide an update about the necessity/frequency of

pre-established conservative therapies. If an AE is suspected based on change in pain scores or functionality, an appropriate work-up will be performed which may include MRI.

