9.2 Recording of Adverse Events

Research subjects will be questioned about adverse effects in person or by telephone the day following the procedure. In addition they will be given a pager number to reach a physician 24 hours a day to report adverse effects and receive medical advice. The subjects will also be questioned about possible adverse effects at each follow-up visit.

All observed or volunteered adverse effects (serious or non-serious) and abnormal test findings, regardless of treatment group, if applicable, or suspected causal relationship to the investigational device or, if applicable, other study treatment or diagnostic product(s) will be recorded in the subjects' case histories. For all adverse effects, sufficient information will be pursued and/or obtained so as to permit 1) an adequate determination of the outcome of the effect (i.e., whether the effect should be classified as a *serious adverse effect*) and; 2) an assessment of the causal relationship between the adverse effect and the investigational device or, if applicable, the other study treatment or diagnostic product(s).

Adverse effects or abnormal test findings felt to be associated with the investigational device or, if applicable, other study treatment or diagnostic product(s) will be followed until the effect (or its sequelae) or the abnormal test finding resolves or stabilizes at a level acceptable to the investigator-sponsor.

An abnormal test finding will be classified as an *adverse effect* if one or more of the following criteria are met:

- The test finding is accompanied by clinical symptoms
- The test finding necessitates additional diagnostic evaluation(s) or medical/surgical intervention; including significant additional concomitant drug treatment or other therapy

- Note: simply repeating a test finding, in the absence of any of the other listed criteria, does not constitute an adverse effect.
- The test finding leads to a change in study protocol or discontinuation of subject participation in the clinical research study
- The test finding is considered an adverse effect by the Sponsor-Investigator.

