10.1 Data Handling and Record Keeping

10.2 Confidentiality

Information about study subjects will be kept confidential and managed according to the requirements of the Health Insurance Portability and Accountability Act of 1996 (HIPAA). Consistent with these regulations a signed authorization will be obtained that informs each subject of the following:

- What protected health information (PHI) will be collected from subjects in this study
- Who will have access to that information and why

- Who will use or disclose that information
- The rights of a research subject to revoke their authorization for use of their PHI.

In the event that a subject revokes authorization to collect or use PHI, the investigator, by regulation, retains the ability to use all information collected prior to the revocation of subject authorization. For subjects that have revoked authorization to collect or use PHI, attempts should be made to obtain permission to collect at least vital status (i.e. that the subject is alive) at the end of their scheduled study period.

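### The removal rule in 4.6.1 ties leaving the study to a major complication without separating the end of the procedure from the end of follow-up, so the 6-month efficacy result can lose subjects because of harm.

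*Combined protocol and SAP*

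**What the plan says.** Section 4.6.1 opens with "Subjects will be withdrawn from the study if" and gives two grounds. One is the subject's own decision. The other is that "a major complication occurs that prevents completion of GAE or the ability to complete the follow up visits". The second ground has two limbs: the procedure could not be completed, or the follow-up visits cannot be completed.

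Section 4.6.2 deals with withdrawn subjects in two sentences: "If a subject withdraws from the study, any recorded data will still be included in the analysis" and "Subjects will only be replaced if they withdrew prior to undergoing GAE". It neither plans nor forbids outcome collection after withdrawal.

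The visit schedule is more flexible than the removal rule suggests. For the 3-month visit, section 6.5 lets subjects be "contacted by phone or by teleconference per the subject's preference 90 +/- 10 days following GAE". For the 6-month visit, section 6.6 says "Subjects will be seen in clinic or contacted by phone or by teleconference per the subject's preference 180 +/- 10 days following GAE". WOMAC and VAS are completed at both. Only the 1-month visit (6.4, day 30 ± 7, with MRI) is confined to the clinic.

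Section 8.2 plans a paired t-test of change from baseline to 6 months. For missing values it asks only that the causes be documented. Section 8.3 requires that an evaluable subject consented, met the entry criteria and had the study procedure. It includes everyone with 6-month data even if other follow-up is incomplete.

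**The concern.** The only removal rule not in the subject's hands is triggered by a bad result of the intervention. Stopping a procedure and leaving a study are different events, and only the first need follow from a complication. Because 4.6.1 merges them, a stated rule, and not just ordinary drop-out, can turn a harmed subject into a missing 6-month outcome. Nothing in 8.2 or 8.3 then brings that subject back into the efficacy result.

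Missingness of this kind depends on outcome. If the removed subjects would have done worse than the rest, the 6-month WOMAC and VAS results look better than those of all subjects in whom GAE was started. Section 2.0 also intends the data for planning a future study, so the bias would carry into that design.

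**Working it through.** **Who is removed, reading the sections together**

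1. *GAE not completed because of a major complication.* The first limb of 4.6.1 applies whether or not the subject can be reached. Nothing in 6.5 or 6.6 provides an exception. Sections 4.6.2 (replacement) and 8.3 (evaluability) do not say whether a started but unfinished procedure counts as GAE. Such a subject could be withdrawn, judged non-evaluable and even replaced.
2. *GAE completed, but a complication keeps the subject from the clinic between days 23 and 37 (30 ± 7).* The 1-month visit with MRI cannot be completed. The second limb refers to the visits in the plural, so one site could withdraw this subject while another phones at 6 months. The text does not settle it.
3. *GAE completed, major complication, all visits possible in some permitted form.* The rule does not apply, and the subject stays in.

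The firm case is 1, case 2 depends on the reading, and case 3 is unaffected.

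**The plan's own sample-size figure**

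Inputs from 8.1: baseline WOMAC 48.5; 16% of this is 0.16 × 48.5 = 7.76, given as 7.8; SD 10, taken here as the SD of the paired change; 80% power with 15 subjects. Alpha is 0.05 (8.2). Sidedness is not stated, and two-sided is assumed.

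Paired t-test, noncentral t distribution with noncentrality (7.8/10) × √n:

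- n = 15: 0.78 × √15 = 3.02, power 80.2%. The stated figure is reproduced. (A one-sided test would give 89%, so two-sided is the matching reading.)
- n = 20: power 91.1%
- n = 19: power 89.5%
- n = 18: power 87.6%

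Losing one or two of 20 therefore costs at most 91.1 − 87.6 = 3.5 percentage points of power. Power is not the problem.

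**Size of the bias (illustration)**

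Assumptions, none of them from the documents except the 7.8 points and the 20 subjects: the remaining subjects improve by a mean of 7.8; k of 20 treated subjects are removed and not replaced; the removed subjects would have shown a mean improvement L, with L = 0 (no change) or L = −7.8 (worse by 7.8).

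Mean over all 20 = [(20 − k) × 7.8 + k × L] / 20. Overstatement = 7.8 minus that mean.

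| k | L | Mean over all 20 | Overstatement |
|---|---|---|---|
| 1 | 0 | 148.2/20 = 7.41 | 0.39 |
| 1 | −7.8 | 140.4/20 = 7.02 | 0.78 |
| 2 | 0 | 140.4/20 = 7.02 | 0.78 |
| 2 | −7.8 | 124.8/20 = 6.24 | 1.56 |

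On the responder scale, an assumed completer rate of 80% becomes 80% × 19/20 = 76% with one removed subject counted as a failure, and 80% × 18/20 = 72% with two.

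**The case against.** The strongest reply is that the second limb applies only when a subject is unable to complete visits, and a phone contact is itself a permitted 6-month visit. A subject who can answer the phone is then not caught, and one who cannot would be missing under any rule. Section 8.3 adds that missed visits are followed up by phone and that incomplete data do not exclude a subject. This largely stands. A reader might infer that every disabling complication costs the 6-month outcome by rule, and the documents do not support that. The reply does not reach the first limb, however, and leaves the clinic-only 1-month visit open to different readings.

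A reader might also infer that removed subjects are abandoned, especially since 10.2 says that for those who revoke authorization "attempts should be made to obtain permission to collect at least vital status". The documents contradict this. Section 11.1.2 has withdrawing subjects asked for their reason, 11.1.6 has all subjects phoned at closure, and 9.2 (Recording of Adverse Events) says device-associated effects "will be followed until the effect (or its sequelae) or the abnormal test finding resolves or stabilizes". Nor can it be said that late consequences of a complication are left out, because that follow-up covers sequelae and has no exception for withdrawn subjects. The complication also counts toward the safety endpoint in 3.4. What is not planned after withdrawal is narrower: WOMAC, VAS and therapy use.

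Finally, the number affected may be zero. The small knee embolization series summarised in 1.2 report no major complications. The rule in 9.5, which stops the study after more than one Grade D, E or F complication, is a limit and not an expected count. Section 4.6.1 does not tie its term to those grades either. This stands, and it is why the figures are illustrative only.

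**Conclusion.** The point holds in a limited form. Section 4.6.1 mandates leaving the study where only the end of the procedure need follow, and 4.6.2 and 8.3 do nothing to recover the 6-month outcome. This is firm when a major complication prevents completion of GAE, and plausible when it prevents the 1-month clinic visit. Any resulting bias favours GAE provided the removed subjects would have done worse than the rest, which is an assumption, though a natural one.

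The size is small: about 0.4 to 1.6 WOMAC points on an assumed 7.8-point improvement if one or two of 20 are removed, and nothing if none are. The safety result is not undermined. The change is still worth making, because the loss is created by the protocol's own wording and can be avoided with contact routes it already provides.

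**What to change.** These changes concern data collection and analysis only. They leave clinical decisions about stopping a procedure as they are.

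- **4.6.1:** State that a major complication does not by itself end study follow-up. Every subject in whom GAE was started stays in follow-up unless consent is withdrawn. WOMAC, VAS, therapy-use and adverse-event data are sought at 1, 3 and 6 months, by phone if the subject cannot attend.
- **4.6.2:** State that a subject with a started but incomplete GAE is not replaced, and that outcome collection continues as above.
- **8.3:** Include subjects with a started but incomplete GAE in the analysis set.
- **8.2:** Add a sensitivity analysis of the 6-month response that counts subjects without 6-month data after a major complication as non-responders.

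The cost is amendment wording, a line in the consent form, a few phone calls, and possibly a slightly less favourable efficacy result.
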